12.3.1 Informed Consent

Informed consent will only be required for Q5 – the following statements apply to this part of the study only.

The Investigator is responsible for ensuring informed consent is obtained before any protocol specific procedures are carried out. The decision of a participant to participate in clinical research is voluntary and should be based on a clear understanding of what is involved.

Participants must receive adequate oral and written information – appropriate Participant Information and Informed Consent Forms will be provided. The oral explanation to the participant will be performed by the Investigator or qualified delegated person, and must cover all the elements specified in the Participant Information Sheet and Consent Form.

The participant must be given every opportunity to clarify any points they do not understand and, if necessary, ask for more information. The participant must be given sufficient time to consider the information provided. It should be emphasised that the participant may withdraw their consent to participate at any time without loss of benefits to which they otherwise would be entitled.

The participant will be informed and (if the participant is a patient) agree to their medical records being inspected by regulatory authorities and representatives of the sponsor(s) but understand that their name will not be disclosed outside the hospital.

The Investigator or delegated member of the trial team and the participant will sign and date the Informed Consent Form(s) to confirm that consent has been obtained. The participant will receive a copy of this document and a copy filed in the Investigator Site File (ISF) and participant's medical notes.

12.3.2 Study Site Staff

The local study investigator is expected to be familiar with the protocol and the study requirements and to publicise the study in their centre. It is the Investigator's responsibility to ensure that all staff assisting with the study are adequately informed about the protocol and their trial related duties.

12.3.3 Confidentiality

All evaluation forms, reports, and other records must be identified in a manner designed to maintain participant confidentiality. All records must be kept in a secure storage area with limited access. The Investigator and study site staff involved with this study may not disclose or use for any purpose other than performance of the study, any data, record, or other unpublished, confidential information disclosed to those individuals for the purpose of the study. Prior written agreement from the sponsor or its designee must be obtained for the disclosure of any said confidential information to other parties.

12.3.4 Data Protection

All Investigators and study site staff involved with this study must comply with the requirements of the Data Protection Act 1998 with regard to the collection, storage, processing and disclosure of personal information and will uphold the Act's core principles.

Access to collated participant data will be restricted.

Computers used to collate the data will have limited access measures via user names and passwords.

Published results will not contain any personal data that could allow identification of individual participants.

13 STUDY CONDUCT RESPONSIBILITIES

13.1 PROTOCOL AMENDMENTS

Any changes in research activity, except those necessary to remove an apparent, immediate hazard to the participant in the case of an urgent safety measure, must be reviewed and approved by the Chief Investigator and Sponsor.

Amendments to the protocol must be submitted in writing to the appropriate REC and local R&D for approval prior to participants being enrolled into an amended protocol.

13.2 PROTOCOL VIOLATIONS AND DEVIATIONS

Investigators will not implement any deviation from the protocol without agreement from the Chief Investigator and appropriate REC and R&D approval except where necessary to eliminate an immediate hazard to trial participants.

In the event that an Investigator needs to deviate from the protocol, the nature of and reasons for the deviation will be recorded. If this necessitates a subsequent protocol amendment, this should be submitted to the REC, and local R&D for review and approval if appropriate.

13.3 SERIOUS BREACH REQUIREMENTS

A serious breach is a breach which is likely to effect to a significant degree:

- (a) the safety or physical or mental integrity of the participants of the trial; or
- b) the scientific value of the trial.

If a potential serious breach is identified by the Chief investigator, Principal Investigator or delegates, the co-sponsors ([contact]) must be notified within 24 hours. It is the responsibility of the co-sponsors to assess the impact of the breach on the scientific value of the trial, to determine whether the incident constitutes a serious breach and, if so, report it to the REC.

All violations will be assessed by the sponsor(s) to ascertain if they meet the criteria for a serious breach. If the sponsor(s) deem the incident to be a violation that does not constitute a serious breach from the protocol when identified, corrective and preventative actions will be taken where appropriate and they will be recorded in file notes, held within the TMF and ISF.

13.4 STUDY RECORD RETENTION

All study documentation will be kept for a minimum of 5 years from the protocol defined end of study point. When the minimum retention period has elapsed, study documentation will not be destroyed without permission from the sponsor.

13.5 END OF STUDY

The end of study date will be finalised in the protocol once the study starts

The Investigators and/or the trial steering committee and/or the co-sponsor(s) have the right at any time to terminate the study for clinical or administrative reasons.

The end of the study will be reported to the REC within 90 days, or 15 days if the study is terminated prematurely. The Investigators will inform participants of the premature study closure and ensure that the appropriate follow up is arranged for all participants involved.

A summary report of the study will be provided to the REC and Regulatory Authority within 1 year of the end of the study.

13.6 INSURANCE AND INDEMNITY

The co-sponsors are responsible for ensuring proper provision has been made for insurance or indemnity to cover their liability and the liability of the Chief Investigator and staff.

The following arrangements are in place to fulfil the co-sponsors' responsibilities:

- The Protocol has been designed by the Chief Investigator and researchers employed by the University and collaborators. The University has insurance in place (which includes no-fault compensation) for negligent harm caused by poor protocol design by the Chief Investigator and researchers employed by the University.

- Sites participating in the study will be liable for clinical negligence and other negligent harm to individuals taking part in the study and covered by the duty of care owed to them by the sites concerned. The co-sponsors require individual sites participating in the study to arrange for their own insurance or indemnity in respect of these liabilities.
- Sites which are part of the United Kingdom's Nation Health Service will have the benefit of NHS Indemnity.
- Sites out with the United Kingdom will be responsible for arranging their own indemnity or insurance for their participation in the study, as well as for compliance with local law applicable to their participation in the study.

14 REPORTING, PUBLICATIONS AND NOTIFICATION OF RESULTS

14.1 AUTHORSHIP POLICY

Ownership of the data arising from this study resides with the study team. On completion of the study, the study data will be analysed and tabulated, and a clinical study report will be prepared in accordance with GCP guidelines.

14.2 PUBLICATION

The clinical study report will be used for publication and presentation at scientific meetings. Investigators have the right to publish orally or in writing the results of the study.

Summaries of results will also be made available to Investigators for dissemination within their clinics (where appropriate and according to their discretion).

14.3 PEER REVIEW

This project has been peer reviewed internally, and was externally peer reviewed during the process of securing funding from the CSO.

APPENDIX 3: INFORMATION FOR WOMEN ABOUT FETAL MOVEMENTS

One of the easiest ways to tell if your baby is healthy is to see how often you can feel her or his movements. Every baby is different, so it is a good idea if you can become familiar with your baby's usual movements and activity, and report to us if you notice a reduction in them. The number of kicks you want to feel per
 	
18-24 WEEKS
 
Most people begin to feel movements between 18-24 weeks if this is a second baby, then you may be aware of these earlier. It may feel like bubbles, flutters or 'the wags'. There are often irregular 'cannys' and gaps. Later you can be sure of more regular hits.
 
Everyone is different. There are many reasons for not feeling movements as early as you expect, including your body weight, your baby's position and the location of your placenta. As long as the baby is growing well at your 22-week check, then you should not worry.

If you feel big, you should become aware of what babies do every day. You should feel movements every day.
 	
24-36 WEEKS
 
'Kicking, punching, stretching and squirming' - these are all words women use to describe their baby's movements. Usually you are more aware of movements when lying down, or at night time, when you are still and often not at all. When you are busy and on your feet.
 
During these weeks, it would be good if you could become aware of what time of day you are most likely to feel movements so you can notice if these become absent or reduced.
 
None of these do not count as movements.

This number of movements may change, but the frequency should not decrease.
 	
36-42 WEEKS
 
At 36-42 weeks, your baby will have less room to wiggle around, and when you get ready to feel the baby, you may notice big movements, and rolling.
 
There will be the nature of the movements may change. But the frequency should not decrease. It should be the same as you feel in the weeks before the date of the check.
 
Some people may tell you that your baby will kick less frequently in late pregnancy and before you go into labour. This is not so. It is important that you report any change, as it might be a sign that your baby is unwell.

APPENDIX 4: UPDATED 09/01/2015

SUGGESTED MANAGEMENT PLAN FOR WOMEN PRESENTING WITH REDUCED FETAL MOVEMENTS

Guideline for management of women presenting with reduced fetal movements at more than 28 weeks gestation.

Suggested management plan is based on that employed in the Tveit study where an intervention was associated with a reduction in stillbirth rates. Given that decreased FM is a risk factor for SGA (OR ranging from 1.6 (1), to 3), these guidelines are also informed by the revised RCOG guidelines on SGA <http://www.rcog.org.uk/files/rcog-corp/GTG31SGA23012013.pdf>. The management plan described here depends very heavily on ultrasound, given data that ultrasound performs well both on an absolute basis and compared with other interventions (with a. ultrasound perceived as useful in detecting abnormalities in 11.6% of scans, b. detection of the identified abnormality being perceived as useful after ascertainment in 86.2% of women and c. the ultrasound being the only modality to detect abnormality in 71.3%). Ultrasound examinations (whether for LV or AC / EFW or umbilical artery Doppler) should only be performed by a trained individual (e.g. RCOG ultrasound module 2 “signed off”), and a formal report issued. Note there is no formal definition of decreased fetal movement – previous studies have suggested that the woman’s perception of decreased fetal movements are the most helpful criterion definition of decreased fetal movement, so that an arbitrary reference range for movements is not recommended).

Single episode of presenting with reduced fetal movement.

i. 37 weeks gestation or more

Assess for risk factors. Perform CTG within 2 hours and USS for LV within 12 hours.

- If CTG abnormal or LV reduced (deepest vertical pool \leq 2cm), arrange delivery, with input from senior obstetrician on timing, and certainly within 48 hours.
- If CTG and LV normal perform USS for EFW /AC next working day (+/-Dopplers as per local protocol).
 - If EFW/AC $>$ 10th centile, growth trajectory normal AND fetal movements have returned to normal, discharge back to routine care.
 - If AC or EFW \leq 10th centile or there is decreased growth velocity or abnormal Doppler deliver with input from senior obstetrician on timing, and certainly within 48 hours.
 - If all investigations are normal but fetal movements have not returned to normal within 24 hours follow recurrent reduced fetal movement pathway.
- If \geq 40 weeks, consider delivery within 48 hours as an alternative to USS.

ii If 27+0 – 36+6 weeks.

Assess for risk factors. Perform CTG within 2 hours and USS for LV within 12 hours.

- If CTG abnormal or LV reduced (deepest vertical pool \leq 2cm), involve senior obstetrician in management plan.
- If CTG and LV normal perform USS for EFW /AC next working day (+/- Dopplers as per local protocol).
 - If EFW/AC $>$ 10th centile, growth trajectory normal AND fetal movements have returned to normal discharge back to routine care.
 - If AC or EFW \leq 10th centile or there is decreased growth velocity or abnormal Doppler review by senior obstetrician as per local protocol for suspected FGR. The revised RCOG guidelines for SGA <http://www.rcog.org.uk/files/rcog-corp/GTG31SGA23012013.pdf> should also be consulted. Consider delivery by 37 weeks for women with suspected fetal growth restriction.

- If all normal but fetal movements have not returned to normal within 24 hours, follow recurrent reduced fetal movement pathway.

iii. If 24+0 – 26+6 weeks.

Assess for risk factors. Confirm fetal viability. Perform fetal anomaly scan if not already completed. If risk factors or FGR and stillbirth present, arrange serial growth USS as per local policy/RCOG guideline.

Recurrent episodes of reduced fetal movement.

Recurrent reduced fetal movement is defined as persistent reduced fetal movement for more than 24 hours or second or subsequent episode within 21 days of first presentation. If previous attendance \geq 21 days ago follow single episode guidance above.

iv. 37+0 weeks gestation or more

Perform CTG within 2 hours. Offer delivery (eg induction of labour) with input from senior obstetrician on timing (and certainly within 48 hours) if woman wishes delivery.

v. 27+0 – 36+6 weeks inclusive.

Perform CTG within 2 hours and LV within 12 hours of presentation. Schedule repeat USS scan for EFW/AC if it is \geq 21 days after previous USS (+/- Dopplers as per local protocol) and perform twice weekly CTG monitoring and weekly LV until then. Thereafter, manage according to repeat scan results. If measurements of EFW/AC are \leq 10th centile, or if there is decreased growth velocity, or abnormal Doppler review by senior obstetrician. If EFW/AC are $>$ 10th centile, return to routine care.

vi. 24+0 – 26+6 weeks inclusive.

Assess for risk factors for stillbirth and FGR. Confirm fetal viability. Perform anomaly scan, if not already done. If high risk of FGR arrange serial growth USS as per local policy /RCOG guideline.

What would the impact of this be on the clinical service?

In addition to a reduction in stillbirth, Tveit (1) showed that a policy of encouraging women to attend quickly after perception of decreased fetal movements had no significant increase in the total proportion of women attending with 6.2% of women presenting with decreased FM in third trimester prior to intervention and 6.6% of women after the intervention

However, it had a significant decrease in the proportion of women who waited more than 48 h to come to hospital (49% vs 54%) significant reduction in admission for induction (4.9% vs 7%) significant decrease in the number of admissions (11% vs 14%) non significant increase in the proportion of women with no follow up (69% vs 63%) a significant increase in the proportion of consultations which had ultrasound (94% compared with 86%).

In two other studies looking at the number of people attending with recurrent decreased fetal movements after 37 weeks, the figures were 0.2 – 0.5% of the obstetric population (2) (3). Again, Tveit showed that his intervention did not increase the number of women presenting, so the figure of 0.2 – 0.5% of the obstetric population should be robust. Even assuming an increase in the proportion of women presenting (at worst a doubling), this would result in only a modest increase in the proportion of women undergoing induction of labour (at worst, 0.4 - 1% of the obstetric population). In practice, the majority may have abnormal growth monitoring, so may already be undergoing induction of labour. These data suggest that, with the exception of the need for ultrasound, these policies should not increase the need for service delivery. Regarding ultrasound, in the worst case scenario (assuming that no woman presenting with reduced FM currently has USS, but that all women will in the future, and assuming that 6-7% of all women will present at some point in the third trimester after the intervention, then a hospital with 7000 deliveries per year will do no more than 2 - 8 extra scans per week. For induction of labour, a hospital with 7000 women would have no more than 0.4 – 1.3 inductions per week.

References:

APPENDIX 5: AUDIT OF COMPLIANCE ADDED 17th July 2017

An audit of compliance with the affirm management protocol (appendix 4: updated 09/01/2015) for women presenting with reduced fetal movements will be determined by two means:

A) **QUESTIONNAIRE** Via Telephone or email contact with Principal Investigators at each site to determine which aspects of the AFFIRM protocol have been implemented effectively.

This will involve email contact with Principal Investigators to alert them to the request for information, detailing the information required, followed by a phone call to elicit the information (unless it had already been supplied). Investigators will be asked which of the following elements they had implemented locally:

- Issuing leaflets to all pregnant women,
- Cardiotocography within 2 hours of presentation,
- Measurement of amniotic fluid volume within 12 hours of presentation,
- Growth scan by the next working day for all women presenting with reduced fetal movement (and who had not had a growth scan within the last three weeks, or who were not being induced within 48 hours),
- Induction of labour within 48 hours for women presenting with recurrent reduced fetal movement at or after 37 weeks gestation.

Compliance (effective implementation) will be defined as 4/5 of the above management elements for 80% or more of the time.

AUDIT PART A: STAFF QUESTIONNAIRE

Dear (PI Name)

You very kindly agreed to answer some questions regarding your unit's compliance with the AFFIRM audit. We would be most grateful to receive your views on the following:

1. In your opinion, were the following aspects of the AFFIRM audit implemented at least 80% of the time at [Insert site name]?

Unit name: (Hospital name)	Yes	Partially	No	If Partially or NO, What proportion of women do you estimate received these?
Leaflets about RFM issued to women				
eLearning completed by staff				
CTG within 2 hours of presentation with RFM				
Growth scans for RFM (next working day)				
IOL for women 37 weeks and above with recurrent RFM (within 48hrs)				

2. If you could turn back time to 1st January 2014, and (with the benefit of experience) would you agree to participate in the AFFIRM study again? YES/NO

If NO, please could you explain why not?

We would be most grateful to receive your answers by **XX/ XXX/XXXX** If you haven't already given us your best address for sending out your vouchers, please don't forget to include this.

As always, thank you so much for your help with AFFIRM.

Best Wishes

[name] and [name]
On behalf of the AFFIRM Study

NB: If you wish to print and fax your completed sheet to us, the number is [name]

B) **CLINICAL AUDIT** to determine whether the perception of the site Principal Investigator is supported by review of actual decision making will be performed for the following elements:

- Cardiocography within 2 hours of presentation,
- Measurement of amniotic fluid volume within 12 hours of presentation,
- Growth scan by the next working day for all women presenting with reduced fetal movement (and who had not had a growth scan within the last three weeks, or who were not being induced within 48 hours),
- Induction of labour within 48 hours for women presenting with recurrent reduced fetal movement at or after 37 weeks gestation.

This will be conducted by asking sites to complete an audit of the management of all women presenting with reduced fetal movement over the course of one calendar month. Sites will be asked to complete an audit form for each participant.

The audit form template (see below) has been generated by the central AFFIRM study team; anonymized forms will be analysed centrally. There will not be an attempt to corroborate Principal Investigator perception of the proportion of women who were given leaflets, nor will there be any attempt to incorporate the proportion of staff who had completed the e-learning package into analysis of whether any specific site has implemented the intervention or not.

AUDIT PART B: CLINICAL AUDIT FORM - One month data collection AUDIT [Month & Year] Unit name: [Name of Hospital]

If you assess a woman with reduced fetal movements (RFM), please complete the questions below. Do not worry if the woman has been seen in other areas of the hospital by other staff, we would rather have multiple reports for the same woman than miss episodes of RFM.

INSERT Patient Sticker (or WRITE name and CHI /NHS number)				AREA WHERE SEEN (CIRCLE)						
				Triage / Labour ward / Day Assessment Unit (DAU)						
				Other (specify area i.e. antenatal ward): _____						
Date and time of presentation with reduced fetal movements.	DATE: ____/____/____ TIME ____:____ am / pm			GESTATION AND EDD:	____ WEEKS ____ DAYS EDD: _____					
Referred by (TICK BOX):	Self	Community Midwife	GP	ANC	Triage	DAU	Other (specify: _____)			
What was the primary reason for attending/phoning? (TICK BOX):	Reduced Fetal Movements			Other (specify: _____)						
How many times has the woman attended before this visit, with RFM? (TICK BOX):	None – first attendance		Once previously	Unknown	Multiple times (please provide the gestation at each presentation i.e. 30+6)	1	2	3	4	5
What was the time interval from the woman first being aware of reduced fetal movements and attending the hospital (in hours)?					HOURS: _____					
Has she been given a leaflet "Your baby's movements in pregnancy"? (TICK BOX):	Yes – she already has one		Yes – I have given one to her today		Locally Created Leaflet Given			NO		
Has this woman had a growth USS in this pregnancy? (TICK BOX):	No, she has not had a growth scan		Yes, within the last 3 weeks (date of scan): DATE: ____/____/____		Yes, but more than 3 weeks ago (date of scan): DATE: ____/____/____					

Can Promoting **A**wareness of **F**etal movements and **F**ocussing **I**nterventions **R**educe **F**etal **M**ortality - a stepped wedge cluster randomised trial? **AFFIRM**

CONTINUATION: NHS/ CHI NUMBER:

Are any of the following risk factors for Fetal growth restriction present (CIRCLE all that apply)?							
Age ≥40 or ≤16	Smoker ≥20cpd	Known or suspected growth restriction	Congenital anomaly	Raised BP (essential hypertension, pre-eclampsia or pregnancy induced hypertension)	Previous pre-eclampsia	Diabetes or gestational diabetes	Previous FGR or stillbirth
What investigations were conducted during this episode of reduced fetal movement?							
Please record below the date and time that these investigations were completed or indicate if not performed.					Please provide the results (CIRCLE):		
CTG	Not performed		DATE: __/__/____	TIME: ____:____ am/pm	Normal / Suspicious / Pathological		
					Computerised CTG: YES / NO (CIRCLE)		
Liquor volume assessment on scan	Not performed		DATE: __/__/____	TIME: ____:____ am/pm	Normal / Reduced / Increased		
Growth scan	Not performed		DATE: __/__/____	TIME: ____:____ am/pm	Normal / EFW < 10 th centile / AC < 10 th centile / EFW and AC < 10 th centile		
Umbilical Artery Doppler	Not performed		DATE: __/__/____	TIME: ____:____ am/pm	Normal / > 95 th centile / absent EDF / reversed EDF		
MCA Doppler	Not performed		DATE: __/__/____	TIME: ____:____ am/pm	Normal / < 5 th centile		
DELIVERY METHOD (If available)							
Was the woman offered induction of labour	YES / NO (CIRCLE)			DATE: ____/ ____/ ____			
	IF Yes, please provide date, time and method of the induction:			TIME: ____:____ am/pm			
Was the woman offered elective caesarean section as a result of the reduced fetal movement?	YES / NO (CIRCLE)			DATE: ____/ ____/ ____		Please provide the reason for the elective Caesarean section:	
	IF Yes, please provide date, time and reason:			TIME: ____:____ am/pm

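### For recurrent reduced movements at term, the compliance audit scores induction carried out, but the plan it audits asks sites to offer delivery if the woman wishes it (minor)

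*Protocol*

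**What the plan says.** Appendix 5 of the protocol states that it audits compliance with the Appendix 4 management plan. It lists five elements: leaflets, CTG, amniotic fluid volume, growth scan and, for recurrent reduced movements at term, "Induction of labour within 48 hours for women presenting with recurrent reduced fetal movement at or after 37 weeks gestation". The Part B (clinical audit) list repeats that element in the same words. The Part A questionnaire row is "IOL for women 37 weeks and above with recurrent RFM (within 48hrs", and its last column asks "What proportion of women do you estimate received these".

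The scoring rule is "Compliance (effective implementation) will be defined as 4/5 of the above management elements for 80% or more of the time".

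The instruction being audited is item iv of Appendix 4 (recurrent episodes, 37+0 weeks or more). After a CTG within 2 hours, it says "Offer delivery (eg induction of labour) with input from senior obstetrician on timing (and certainly within 48 hours) if woman wishes delivery".

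Part B exists "to determine whether the perception of the site Principal Investigator is supported by review of actual decision making". Its form includes the item "Was the woman offered induction of labour", followed by the date, time and method of the induction, and a separate item on whether elective caesarean was offered.

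**The concern.** The audited behaviour and the scored behaviour differ in three ways. The plan asks for an offer, makes delivery conditional on the woman's wish, and treats induction as one possible route. The audit element drops all three.

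A site that follows Appendix 4 exactly can therefore be scored as missing the element, and its effective-implementation label can be understated. The element also loses diagnostic value. A low score could mean that clinicians did not offer delivery or that women declined it, and these call for different responses. The protocol gives a reason to want them apart: in the 2012 Scottish survey (section 1.1), nearly 25% of respondents said they would never offer induction before 41 weeks to women at term with more than one episode.

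**Working it through.** The plan states no figure to reproduce. The check sets the texts side by side and follows the scoring rule through.

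**1. Plan against element**

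- Action: Appendix 4 iv asks for an offer; Appendix 5 scores induction done.
- Condition: Appendix 4 iv applies if the woman wishes delivery; Appendix 5 has no condition.
- Route: Appendix 4 iv means delivery, with induction as an example; Appendix 5 counts induction only.
- Time: 48 hours in both.

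The growth-scan element in the same list does carry written exceptions, for women "and who had not had a growth scan within the last three weeks, or who were not being induced within 48 hours". The induction element carries none.

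**2. When the element fails**

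Let *o* be the share of eligible women (recurrent reduced movements, 37 weeks or more) who are offered delivery. Let *a* be the share of those offered who are induced within 48 hours. Read literally, the element's score is *o* × *a*.

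- A site that offers to everyone has *o* = 1, so its score is *a*. It fails when *a* < 80%, that is, when more than 100% − 80% = 20% of eligible women are not induced within 48 hours.
- If the element counted an offer that was declined, or delivery by any route within 48 hours, a site that offers to all and delivers in time those who accept would score 100% whatever the uptake.
- Illustration with an assumed 70%: offering to all with 70% induced gives 1 × 0.70 = 70%. Offering to 70% with all of them induced gives 0.70 × 1 = 70%. The scores are equal, but only the first site followed the plan.

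**3. When the label changes**

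The rule needs four of five elements, so 5 − 4 = 1 may be missed. I read it at site level, because Appendix 5 asks investigators what was implemented locally and speaks of whether a given site implemented the intervention.

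- Other four met: 4 + 0 = 4, compliant even if this element is missed.
- Three of the other four met: 3 + 1 = 4 is compliant, 3 + 0 = 3 is not. Here the element decides.
- Two or fewer of the others met: at most 2 + 1 = 3, not compliant either way.

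**4. How much slack there is in Part A**

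The printed Part A table has rows for leaflets, eLearning, CTG, growth scans and induction. It has no row for amniotic fluid volume, and Appendix 5 keeps eLearning out of the judgement of whether a site implemented the intervention. That leaves 5 − 1 = 4 elements with a row, and four are needed, so the spare is 4 − 4 = 0. Unless fluid volume is obtained by telephone or email, or from the Part B form (which records it), a site must meet all four, including induction.

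**5. What uses the label**

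SAP section 9.4 builds the on-treatment variable from when the intervention was actually implemented at a site, and section 9.5.1 uses that variable. Neither section, nor the primary model in 9.5, refers to the 4/5 rule.

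**The case against.** The case against acting has several parts.

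- **Receipt is a defensible fidelity measure.** The trial's hypothesis depends on timely delivery, so what women received is of interest. That stands as a reason to keep reporting receipt. It does not make receipt a measure of compliance with a plan that asks for an offer.
- **The rule has tolerance.** The 80% threshold and the one permitted miss absorb moderate refusal. This stands and limits the effect, although the permitted miss disappears if fluid volume is not obtained for the Part A count.
- **Part B already asks about offers.** This is largely right: the form separates offered from not offered. But the listed element is still induction within 48 hours, the form dates the induction rather than the offer, and the form text available shows no item for declining. Two analysts could score the same form differently.
- **The growth-scan exceptions are clinical, and the CTG and fluid-volume elements have no refusal clause either.** True, so the contrast within the list is modest. However, Appendix 4 attaches no condition about the woman's wish to CTG or fluid volume. It does so in item iv, and that condition was lost.
- **The survey figure is stated intention from before the trial.** Agreed. It shows why non-offering is worth detecting, not that active-phase sites failed to offer.

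**Conclusion.** The mismatch is real and wrong as written, but minor. Taken literally, the element can count against a site that followed Appendix 4, and it merges clinicians not offering with women declining. The effect is confined to the descriptive, site-level effective-implementation label. It needs both more than 20% of eligible women not induced within 48 hours and a miss on another element. The documents give no refusal rate, so the number of sites affected cannot be estimated.

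This rests on reading the 4/5 rule at site level with the 80% cut-off applied to each element.

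A reader might infer more, and the documents do not support it:

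- *That the primary or on-treatment result is biased.* Neither analysis uses the audit score. SAP 9.4 also mentions a compliant intervention period, but does not say that it comes from the audit.
- *That refusals alone make a site non-compliant.* With the other four elements met and counted, the label does not change.

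**What to change.** Reword the element in both lists and the Part A row along these lines: *delivery (e.g. induction) offered to women with recurrent reduced movements at or after 37 weeks, and carried out within 48 hours if the woman wishes*. Score it as met if delivery was offered and was either declined or carried out within 48 hours by any route.

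On the Part B form, add a tick-box for declining beside the existing offer items. Tabulate offers and deliveries within 48 hours separately, so that receipt is still reported. For forms already returned, show women offered delivery with no date recorded as their own row. It would also help to say where the fluid-volume answer comes from in the site count.

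The cost is one element reworded in three places and one tick-box. No SAP analysis changes.
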